### *Participants*

N=28 male and female participants diagnosed with vocal fold atrophy. 14 patients will be recruited for each arm of the study.

### *Inclusion/Exclusion*

Age 65 years or older with chief complaint of a voice problem with VHI-10  $\geq 1$ . Primary diagnosis of vocal fold atrophy only as determined by a multi-disciplinary team of fellowship-trained laryngologist and voice-specialized speech-language pathologist, and willingness to be randomized to treatment option. No concomitant laryngeal diagnoses or diseases known to affect voice function, including: amyloidosis, arytenoid dislocation, laryngeal cancer, cricoarytenoid fixation, vocal fold cyst(s), vocal nodules, vocal fold polyp(s), dysplasia, vocal fold fibrous mass(es), glottal web, vocal fold immobility, laryngeal stenosis, laryngocele, leukoplakia,

Parkinson’s disease, Reinke’s edema, respiratory recurrent pneumonia, sarcoidosis, spasmodic dysphonia; any chronic lower airway disease such as chronic obstructive pulmonary disease (COPD), asthma, chronic bronchitis, emphysema, cystic fibrosis; history of acute stroke, untreated hypertension, or untreated gastroesophageal reflux disease (GERD).

*Consent*

A trained study team member will be responsible for recruiting patients. On the day of their first visit, the informed consent will be obtained. The informed consent process will occur in a private room before starting any therapy. The participants will be randomized to either of the study arms, if they consent.

**Intervention/Experimental Protocol**

*Outline Of Procedures*

The experimental protocol consists of pre-treatment and post-treatment acoustic and aerodynamic data collection and four 45-minute sessions of voice therapy. All subjects will complete PhoRTE therapy, and those in the EMST+PhoRTE arm in the study will also undergo EMST training. Before each PhoRTE therapy, subjects will report to the PI so that therapists are blinded as to which treatment group each subject is in.

Baseline	Therapy 1	Therapy 2	Therapy 3	Therapy 4	Post-Tx
Pre-Tx Acoustic and Aerodynamic Measurements, VHI-10, AVI, MEP	PhoRTE +/- EMST  VHI-10 MEP	PhoRTE +/- EMST  VHI-10 MEP	PhoRTE +/- EMST  VHI-10 MEP	PhoRTE +/- EMST  VHI-10 MEP	Acoustic and Aerodynamic Measurements, VHI-10, AVI, MEP

*PhoRTE Therapy (Standard of Care Treatment)*

Each therapy session will last for 45 minutes.

1st PhoRTE treatment session

- Check in with your patient about current status
  - o Do you have any questions since we last met? Do you have any concerns about your ability to commit to PhoRTE?
- Check in with the patient to verify implementation of voice care program
  - o Dehydration, non-phonatory inflammation (reflux, illness)
  - o Phonotrauma (throat clearing, cough)
  - o Caffeine
- Provide patients with PhoRTE therapy information sheets, phrase list, and practice sheets
- Set up the patient for home practice
  - o Verify that patient is able to download a decibel meter app successfully, and configure the app’s settings with a sound pressure level meter for home practice

- Orient the patient to the app; teach them how to open and utilize the app for home practice; demonstrate for the patient how to standardize mic-to-mouth distance
- Verify that 10 functional phrases for practice are written. Review phrases for length and that they are representative of typical communication
- Teaching proper breathing form
  - Establish efficient respiratory mechanisms to effectively execute PhoRTE exercises
  - Ex. "Place your hand on your upper abdomen just above your belly button. Now, I want you to sustain the sound "sh" for as long as is comfortable. Notice the inward movement of your hand as you exhale and sustain "sh." Let's practice this breathing a few more times until you feel comfortable with this task."
  - Tip for clinician → monitor for hyper-functional muscle use in the abdomen and throat during these breathing tasks by visually or auditorily identifying any extraneous tension as well as by eliciting patient report
- Teaching increased pulmonary drive
  - Clinician: "Now let's practice the same task but make the "sh" stronger. This type of breathing is what you'll need to effectively exercise your voice during PhoRTE. Notice that your hand moves in further and faster because you have to use more air to produce that "sh" with strength. Let's practice this breathing a few more times until you feel comfortable with the task."

#### Before therapy sessions

- Determine noise level in treatment room
- Position sound level meter 12 inches from patient's mouth
- Sustain /a/ at modal pitch and comfortable loudness; have patient use speaking voice in two takes – Rainbow Passage and monologue of 30-60 sec
- Calculate the patient's vocal intensity range (i.e. maximum dB SPL minus minimum dB SPL)
- The starting PhoRTE vocal exercise target is 50-60% of dynamic range, and add dB SPL amount to average vocal intensity of monologue
- Complete EMST calibration and MEP measurement (see description below)

#### Exercise 1 – Phonation-Respiratory Isotonics (PhoRTE-ISO)

- Clinician: "Place your hand on your upper abdomen. Now, I want you to sustain the sound "ah" with a strong, energized voice for as long as your are able. Your starting vocal intensity is \_\_\_\_dB. You will need to achieve your target vocal intensity and maintain it during the entire "ah" to get maximal benefit from this PhoRTE exercise. I want you to check that your mouth is at the appropriate distance from the app. Let's practice this first PhoRTE exercise a few times until you feel comfortable with the task. Remember to record on your PhoRTE log the length of time you are able to hold each "ah."

### Exercise 2 – Eccentric-Concentric Cricothyroid Contraction (PhoRTE-EC)

- Clinician: “Just like stretching exercises are good for your arms and legs to keep you young and flexible, first we are going to produce an ascending and descending pitch glide with a strong, energized voice without strain. Place your hand back on your upper abdomen. Again, your starting target vocal intensity is \_\_\_\_dB. You will need to achieve your target intensity and maintain it during the entire pitch glide. If you have difficulties achieving a strong, energized voice at the low end of your range, don’t worry. That’s typical. After completing five ascending-descending glides, then reverse and produce five descending-ascending glides with a strong, energized voice without strain.”

### Exercise 3 – Phonation-Respiratory Power Endurance (PhoRTE-PE)

- Exercise A → functional phrases in a higher, energized calling voice
  - o Clinician: “Place your hand back on your upper abdomen. Again, your starting target vocal intensity is \_\_\_\_dB. You will need to achieve your target intensity and maintain it during the production of functional phrases. The first time we are going to say the phrases in a higher pitch with an energized voice as if we are calling to our neighbor by throwing your voice.” (Clinician demonstrates megaphone gesture with hands around mouth). Breathe as you feel necessary but avoid overtly large breaths before each subsequent
- Exercise B → functional phrases in a lower, energized voice of authority
  - o Clinician: “Place your hand back on your upper abdomen. Again, your starting target vocal intensity is \_\_\_\_dB. You will need to achieve your target intensity and maintain it during the production of functional phrases. This time we are going to say them in a lower pitch with an energized voice of authority. Breathe as you feel necessary but avoid overly large breaths before each subsequent sentence.”
- Tips to the clinician
  - o Start at resting expiratory level (the point in the breathing cycle at the end of quiet expiration). Beware they are not breath holding or using a strained/pressed production. The goal is for the patient to increase muscle activity of the abdominal musculature rather than over-utilizing/straining laryngeal musculature. Encourage the patient to, at most, take a small replenishing breath between each phrase.
  - o Natural variability in vocal intensity around the target dB will exist due to differences in speech sound sonority and linguistic stress patterns.
  - o Some patients have more difficulty with the voice of authority (vs. the calling voice). This difficulty may be due to a number of sources: (1) the positive nature of the phrase does not lend itself to a voice of authority, for example, “I love you; (2) structurally, the nature of presbyphonia results in patients using laryngeal compensation to achieve better vocal fold closure, which leads to a higher pitch; (3) some people’s personality or past experiences makes it uncomfortable for the patient to produce a voice of authority. The key for patients is to remember that this manner of production promotes the natural

pitch variability in conversation, and is not meant to conjure up negative feelings or emotions.

- Have the patient observe an appropriate recovery period in which they sit silently for a duration of 10-20 seconds between completion of exercises 3a and 3b. The purpose of the rest period is to, theoretically, clear lactic acid and other short-term metabolic effects of exercise.
- Start at resting expiratory level (the point in the breathing cycle at the end of quiet expiration). Beware they are not breath holding or using a strained/pressed production. The goal is for the patient to increase muscle activity of the abdominal musculature rather than over-utilizing/straining laryngeal musculature. Encourage the patient to, at most, take a small replenishing breath between each phrase.

#### Exercise 4 – Phonation-Respiratory Muscular Endurance-Short (PhoRTE-ME)

- Clinician: “Place your hand back on your upper abdomen. Again, your starting vocal intensity is \_\_\_\_dB. You will need to achieve your target intensity and maintain it while you are speaking. We are going to speak in a strong, energized voice for a minimum of 30 seconds but no more than 2 minutes. Breathe as you feel necessary but avoid overly large breaths before each subsequent sentence.

#### *EMST Training (Study procedure)*

The EMST device will be used to incrementally strengthen the respiratory muscles each week. The device will be calibrated each week using a manometer. Maximum expiratory pressure (MEP) will be measured before beginning each therapy session, and this will be used to calibrate the device for the weekly exercises. The device will be set to 75% of MEP for the week’s exercises.

#### *Recording Baseline and Post-Treatment Acoustic and Aerodynamic Measures*

Participants will read the following sentences/exercises for measurement of acoustic and aerodynamic values:

Acoustic...

- 1) “The blue spot is on the key again.”
- 2) “How hard did he hit him?”
- 3) “We were away a year ago.”
- 4) “We eat eggs every Easter.”
- 5) “My mama makes lemon muffins.”
- 6) “Peter will keep at the park.”

Aerodynamic...

The Rainbow Passage: “When the sunlight strikes raindrops in the air, they act like a prism and form a rainbow. The rainbow is a division of white light into many beautiful colors. These take the shape of a long round arch, with its path high above, and its two ends apparently beyond the horizon. There is, according to legend, a boiling pot of gold at one end.”

Home Practice Forms

☐ PhoRTE target vocal intensity: \_\_\_\_\_ dB  
 ☐ PhoRTE target vocal effort: \_\_\_\_\_ /10

PhoRTE Voice Tasks		Reps	1	2	3	4	5	6	7	8	9	10	Comments
Date	Ex 1 Strong and long PhoRTE ah												
	Ex 2 Pitch glides in PhoRTE voice												
	Ex 3 Phrases in PhoRTE "calling" voice												
	Ex 4 Phrases in PhoRTE "authority" voice												
	Ex 5 Speak w PhoRTE voice for a noisy place												
Date	Ex 1 Strong and long PhoRTE ah												
	Ex 2 Pitch glides in PhoRTE voice												
	Ex 3 Phrases in PhoRTE "calling" voice												
	Ex 4 Phrases in PhoRTE "authority" voice												
	Ex 5 Speak w PhoRTE voice for a noisy place												
Date	Ex 1 Strong and long PhoRTE ah												
	Ex 2 Pitch glides in PhoRTE voice												
	Ex 3 Phrases in PhoRTE "calling" voice												
	Ex 4 Phrases in PhoRTE "authority" voice												
	Ex 5 Speak w PhoRTE voice for a noisy place												
Date	Ex 1 Strong and long PhoRTE ah												
	Ex 2 Pitch glides in PhoRTE voice												
	Ex 3 Phrases in PhoRTE "calling" voice												
	Ex 4 Phrases in PhoRTE "authority" voice												
	Ex 5 Speak w PhoRTE voice for a noisy place												
Date	Ex 1 Strong and long PhoRTE ah												
	Ex 2 Pitch glides in PhoRTE voice												
	Ex 3 Phrases in PhoRTE "calling" voice												
	Ex 4 Phrases in PhoRTE "authority" voice												
	Ex 5 Speak w PhoRTE voice for a noisy place												

Write 10 phrases to speak using your strong PhoRTE voice. See the table below for guidance on writing 10 functional phrases for PhoRTE Exercises 3 and 4.

Good Examples	Poor Examples
Hello, how are you? (5 syllables)	Hello. (too short)
I need my medication. (7 syllables)	I need my blood pressure medication that I take every morning. (too long)
Let's go for a walk this morning. (8 syllables)	Let's watch the solar eclipse. (not representative of daily demands)

1. \_\_\_\_\_

2. \_\_\_\_\_

3. \_\_\_\_\_

4.

\_\_\_\_\_

6. \_\_\_\_\_

7. \_\_\_\_\_

8. \_\_\_\_\_

9. \_\_\_\_\_

10. \_\_\_\_\_

## PhoRTE™ Home Practice Information Sheet

[figure not shown]
Complete 1 set of the PhoRTE voice tasks a total of 6 days per week. Track your progress by recording the results of your practice on the PhoRTE patient charting form.

- Ex 1 Say AH in your strong PhoRTE voice for as long as possible without strain.
- Ex 2 Glide on AH in your strong PhoRTE voice. 5x as low-high-low, 5x as high-low-high.
- Ex 3 Speak your functional phrases in a strong and higher PhoRTE "calling voice".
- Ex 4 Speak your functional phrases in a strong and lower PhoRTE "voice of authority".
- Ex 5 Speak in a strong PhoRTE voice so you can be heard in a noisy restaurant.

### OMNI Vocal Effort Scale

Some people do not have an app or meter to measure vocal intensity during their PhoRTE practice. In that case, use the following OMNI Effort Scale to complete the PhoRTE tasks at your target vocal effort. Always remember to stay at vocal effort level 6 (i.e., *somewhat hard*) when you complete your practice.

*Based on the scale below, use the numbers from 0-10 to indicate how much effort you perceive when using your voice TODAY?*

### Data collection and Management

Research Electronic Data Capture (REDCap), will be used to manage all participant data from initial screening through study completion. Each subject will be given a subject number and patient's identifying information will be stored in the database. Once the data collection is completed, the data will be downloaded from the REDcap application in a way that all personal health identifiers are removed. The deidentified data will be stored in a secure Emory server and shared with University of Pittsburgh for the purpose of analysis. All the personal identifiers will be kept only in REDcap database until the completion of study.

### *Database Design*

Data will be collected and managed through REDcap database. It is a secure web application designed to support data capture for research studies, providing user friendly web-based case reports, data validation and a DE identified data export mechanism to statistical packages such as SAS, SPSS, STATA.

### *Data Entry*

At the start of each therapy session, the study coordinator (PI or Co-I if study coordinator is not available) will have the participant sit in the Voice Research Lab and complete the following outcomes:

- MEP measurement through the manometer
- Complete VHI-10 in REDCap

The study coordinator will enter the following data into REDCap:

- Weekly practice logs for PhoRTE and/or EMST

### *Data Reduction*

The PI will reduce the data according to the following protocol.

### *Acoustic*

The sentence, “we were away a year ago” will be spliced and saved. File name:

**SubjectID\_acoustic\_timepoint. Ex: 06\_acoustic\_week1.**

Next, the ADSV software will be used to compute: CSID, CPP, CPP F0, CPP F0 sd, avg vocal intensity in dB SPL.

Data entered in REDCap.

### *Aerodynamic*

The passage will be reviewed and any errors or pauses deleted. The file will be saved. File name: **SubjID\_aero\_timepoint. Ex: 06\_aero\_week3.**

The User Protocol One software in PAS will be used to calculate Average airflow in speech, average number of breaths, average duration of reading passage.

Data entered in REDCap.

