## **Background and Introduction**

The phonatory and respiratory systems undergo many age-related changes in their anatomy and physiology that can lead to undesirable effects on the voice. These changes have detrimental effects on the lives of elderly individuals. Few studies have evaluated the use of voice therapy treatment options for age-related voice disorders. The aim of this study is to compare a voice therapy program developed specifically for patients diagnosed with presbyphonia, Phonation Resistant Training Exercises (PhoRTE), with and without the addition of an expiratory muscle strength training (EMST) protocol that has been shown to strengthen the expiratory respiratory muscles. We hypothesize that the addition of EMST to PhoRTE is at least as effective as PhoRTE alone in treating vocal fold atrophy in elderly patients.

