### *VHI-10*

The primary outcome is the Voice Handicap Index-10 (VHI-10) score. The VHI-10 is a patient-centered outcome that quantifies a patient's perception of handicap caused by a voice disorder and will be measured at every session. VHI-10 will be anchored to baseline VHI-10 score (each item anchored) for the 1 week follow-up (will be administered without anchoring). Secondary outcomes include the following:

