### *Aerodynamic Measures*

Average airflow in speech, average number of breaths, average duration of a standard reading passage (The Rainbow Passage). Our prior work has demonstrated sensitivity to change following treatment for these acoustic and aerodynamic measures.

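### Deleting pauses from the Rainbow Passage recording before reading duration and number of breaths are calculated can remove a real treatment effect on both secondary outcomes

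*Combined protocol and SAP*

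**What the plan says.** The VHI-10 section names the primary outcome and then introduces a list with "Secondary outcomes include the following". That list includes, under Aerodynamic Measures, "Average airflow in speech, average number of breaths, average duration of a standard reading passage", the passage being the Rainbow Passage. The same section adds: "Our prior work has demonstrated sensitivity to change following treatment for these acoustic and aerodynamic measures".

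The processing is set out under Data Reduction, which opens with "The PI will reduce the data according to the following protocol". Its Aerodynamic part gives the order of work. First, "The passage will be reviewed and any errors or pauses deleted". The file is then saved, and the software is used to "calculate Average airflow in speech, average number of breaths, average duration of reading passage".

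The documents do not say what counts as a pause, do not exempt pauses for breath, and describe no measurement of duration or breaths from an unedited recording. Blinding is stated for the therapists (Outline Of Procedures) and for the perceptual raters (Auditory Perceptual Analysis). It is not stated for this editing step.

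**The concern.** Pauses are part of the time taken to read a passage aloud, and breaths are normally taken in pauses. A rule that removes pauses before these two quantities are measured removes part of what is to be measured.

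This matters more here than in most voice trials. The arms differ only in expiratory muscle training, which the Background says "has been shown to strengthen the expiratory respiratory muscles". If that training changes how often or how long participants stop to breathe, reading duration and breath count are outcomes in which the change could appear. The edit can erase it first. A null result on either outcome could then reflect the processing and not the treatment, and the estimated difference would be affected as well as the test.

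**Working it through.** The plan gives no figure on this point to reproduce. The check is on the order of operations, followed by an illustration.

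**What the edit does.** Edited duration = recorded duration − total length of deleted segments. Edited breath count = recorded breaths − breaths inside deleted segments. Both follow from calculating on the edited file.

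**Inputs from the documents.** 14 participants per arm (Participants); a t-test (Data Analysis Plan); the reading text, which begins "When the sunlight strikes raindrops in the air, they act like a prism and form a rainbow" and has 64 words by count.

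**Inputs assumed.** Speech time 18 to 22 s, i.e. 64/18 × 60 = 213 to 64/22 × 60 = 175 words per minute of articulation; 4 to 8 pauses of 0.4 to 0.8 s; SD of duration 3 to 5 s, meant for either change or post-treatment values because the plan does not say which is tested; two-sided alpha 0.05; treatment changes pausing only, not articulation rate.

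**Shift in level.**
- All pauses cut, low end: 4 × 0.4 = 1.6 s; 1.6/(22 + 1.6) = 6.8% of duration.
- All pauses cut, high end: 8 × 0.8 = 6.4 s; 6.4/(18 + 6.4) = 26.2%.
- Only 1 to 3 hesitations of 0.5 to 1.0 s cut, breath pauses kept: 0.5/(22 + 6.4 + 0.5) = 1.7% to 3.0/(18 + 1.6 + 3.0) = 13.3%.

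A shift that is equal in both arms does not by itself bias the comparison.

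**Loss of signal under identical editing.** Suppose one arm takes 2 to 3 fewer pauses. The true difference is (number of pauses) × (pause length). For the two-sample t-test, df = 26 and noncentrality = (difference/SD) × √(14/2) = (difference/SD) × √7.

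| Fewer pauses × length | True difference | Power, SD 3 s | Power, SD 5 s |
|---|---|---|---|
| 2 × 0.4 s | 0.8 s | 10.4% | 6.9% |
| 3 × 0.4 s | 1.2 s | 17.5% | 9.4% |
| 2 × 0.8 s | 1.6 s | 27.4% | 12.9% |
| 3 × 0.8 s | 2.4 s | 53.1% | 23.1% |

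Once all pauses are deleted, the difference in each row is 0 and the rejection rate is 5%. If each of those pauses held a breath, a true difference of 2 to 3 breaths also becomes 0.

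**If cuts differed by arm.** With no true effect, a 1 s difference in the amount cut gives 13.6% (SD 3 s) to 8.0% (SD 5 s) false positives; 0.5 s gives 7.1% to 5.7%. This shows the scale only. The documents give no evidence that such a difference occurs.

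**The case against.** The strongest reply is that the literal reading sits badly with the plan's own outcome. Breaths are counted from the same edited file, and if every pause were cut that count would mean little. Set beside errors, pauses may mean only interruptions such as a lost place or a restart. The step would then be ordinary cleaning, and duration would mean fluent reading time, which is a legitimate choice. This stands as a possible reading, and under it the harm is smaller and the breath count may be intact. But the text says any pauses, sets no limit, and leaves the choice to the editor.

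The illustration is also soft at its low end. With 0.4 s pauses, power is only about 7% to 17% against 5%. That is correct, and the full range is shown for this reason.

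Cleaning has real value too. Re-reading the 17-word first sentence would add 17/64 × 18 = 4.8 s to 17/64 × 22 = 5.8 s, more than the 0.8 to 2.4 s effects considered. A fully unedited duration is therefore not the best main measure.

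A reader might infer three stronger points that the documents do not support:
- **Biased editing by the PI.** Outline Of Procedures suggests, without stating, that the PI knows the arm, but Data Entry names the coordinator first for the session-start measures, and the file names carry subject and time point, not arm. Differential editing is a possibility, not a finding.
- **Measures chosen for their sensitivity to change.** Aerodynamic Measures reports sensitivity in prior work but does not give it as the reason for choosing them.
- **Distorted average airflow.** The documents do not say how the software treats silence, so nothing can be concluded.

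**Conclusion.** The point holds as a defect in a stated processing rule. Followed literally, the rule shortens duration with every cut, lowers the breath count whenever a cut pause contains a breath, and can remove a real treatment effect on either outcome without any difference in editing between arms.

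The shortening is certain once anything is cut. The effect on the breath count depends on what is treated as a pause. The cost in power cannot be derived from the documents. The range of about 7% to 53% with pauses kept, against 5% with all pauses cut, rests on the assumed pause counts, pause lengths, SD and alpha, and on treatment acting through pausing alone.

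The reach is limited to two secondary outcomes. The primary VHI-10, the AVI, MEP, the acoustic measures (taken from a separate sentence) and the perceptual ratings are untouched. It should be corrected before data reduction begins.

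**What to change.** Change the Aerodynamic instruction under Data Reduction as follows:
- For duration and number of breaths, do not delete pauses, including breath pauses.
- Delete only misread or restarted words, defined in advance and handled identically in all files.
- Retain the original recordings, and report duration from the unedited file as a sensitivity analysis.

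As an optional safeguard, an existing team member other than the PI could recode the files to random IDs without time point before the PI edits them, and hold the key. This is partial protection, since the PI may recognise voices.

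The cost is one changed instruction and, if adopted, one recoding step by existing staff. No participant is excluded and no procedure is added. The small downside is that hesitations stay in the duration and add some noise.
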